Mounting evidence from epidemiology, psychopathology, and genetics challenges the commonly held notion that MDD and BPD are easily distinguishable diagnostic entities. As emphasized by others, there are no obvious “points of rarity” in the symptom continuum between bipolar and unipolar disorders and subsyndromal states (Phelps et al., 2008). The possible clinical implications are large as antidepressants can be of limited benefit in the treatment of DSM-IV BPD, and in some cases, can have disastrous consequences (e.g., El-Mallakh et al., 2006; Sachs et al., 2007).

A central limitation of prior studies seeking to compare Positive Valence Systems (PVS) domains in mood disorders is the reliance on DSM diagnoses, which fails to capture the full dimensional range of a construct. In keeping with the research domain criteria (RDoC), the present proposal avoids this problem by capitalizing on our substantial database of studies using the Probabilistic Reward Task (PRT) to define our sample. First developed in 2005 (Pizzagalli et al., 2005), the PRT allows to objectively assess participants’ propensity to modulate behavior as a function of reward and has been made freely available to 73 research groups (55 US groups, 18 international groups). We have assessed 988 participants using the PRT across 14 studies and 6 independent labs in different countries. This sample includes 821 healthy controls and 167 individuals with current or past unipolar or bipolar mood disorder or elevated depressive

symptoms (current MDD: n=102; past MDD: n=32; past BPD: n=18; elevated depressive symptoms: n=15). Our dataset is large enough to build a normative distribution, ensuring that we can recruit subjects for our neuroimaging measures (n=80) that sample the full range of reward learning performance, without incurring the expense of recruiting a very large sample. Using PRT data from healthy controls (n=821), we can empirically demonstrate two important features: **1)** on a group level, patients with unipolar and bipolar diagnoses show attenuated and potentiated reward learning during this task, respectively, and **2)** DSM diagnostic categories fail to capture subsets of patients from both groups; i.e., some patients with unipolar diagnoses display intact reward learning, and some patients with bipolar diagnoses show disrupted (abnormally high) reward learning

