[** These exclusion criteria are included due to the proposed focus on reward learning, which relies on dopaminergic-rich brain circuitry and would thus be strongly affected by lifetime stimulant dependence and current treatment with methylphenidate or other ADHD medications.]

Inclusion Criteria: Mood Disorder Patients (n = 160)

- 1) Non-psychotic individuals seeking treatment at the Mass General Hospital (MGH) Depression Clinical and Research Program (DCRP), MGH Bipolar Clinical and Research Program (BCRP), and McLean Hospital Bipolar Disorder Program
- 2) Written informed consent;
- 3) Both genders and all ethnic origins, age between 18 and 65;
- 4) Right-handed (Chapman and Chapman, 1987);
- 5) Normal or corrected-to-normal vision and hearing
- 6) Absence of current illicit drug use (cocaine, amphetamines and cannabis) as assessed by urine drug test.
- 7) Stable medication over the past 8 weeks OR absence of any psychotropic medications for at least 2 weeks (for follow-up analyses testing effects in medication-free patients):
 - 6 weeks for fluoxetine,
 - 6 months for neuroleptics,
 - 2 weeks for benzodiazepines,
 - 2 weeks for any other antidepressants
 - 4 weeks for any mood-stabilizers

Inclusion Criteria: Healthy Controls (n = 32)

Absence of medical, neurological, and psychiatric illness (including alcohol and substance abuse), as assessed by subject history and a structured clinical interview (SCID-I/NP).

- 2) No family history of mood disorders;

- 3) Written informed consent;
- 4) Both genders and all ethnic origins, age between 18 and 50;
- 5) Right-handed (Chapman and Chapman, 1987).
- 6) Normal or corrected-to-normal vision and hearing
- 7) Absence of current illicit drug use (cocaine, amphetamines and cannabis) as assessed by urine drug test.
- 8) No psychotropic medication.

b. Source of subjects and recruitment methods

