Aim 2: For Hypothesis 2a, symptom inventories collected during follow-up interviews will be used to investigate incremental predictive validity of each unit of analysis in predicting subsequent symptoms while controlling for baseline severity. For these models, our behavioral and neuroimaging measures will be modeled using the relative weighting derived from the analyses described in aim 1. For quantitative measures (e.g., depressive and anhedonic symptoms), linear mixed effects models will be used. These models incorporate random subject effects to account for correlation among the repeated outcome measures (months 0, 3, 6); models will be fit using SAS PROC MIXED. Hypotheses concerning frequency measures (e.g., frequency of impulsive/risky behaviors) will be tested in a similar way. Models will be fit using SAS PROC GENMOD. Statistical tests and confidence intervals will be based on the “sandwich” estimator of standard errors to ensure that correlation among repeated assessments and overdispersion is accounted for.

d. Power analysis

Sample size and power calculations

Sample size determination was calculated based on observed effect sizes derived from prior studies that in our lab. Effect sizes were calculated using $\alpha = 0.05$ (two-tailed) for (1) detecting relationships between reward learning variables across different unit of analyses and reward-related symptoms (e.g., anhedonia, mania); and (2) to predict symptom severity measures in a naturalistic follow-up study. Based on these estimates and allowing for 15% patient attrition or data loss, the sample will be: 80 treatment-seeking individuals with mood disorders recruited from three clinics as well as 32 psychiatrically healthy controls.

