For group comparisons, multiple past studies using the PRT have found that unmedicated MDD subjects exhibited reduced reward learning compared to controls (Cohen's $d: -0.70$; Pizzagalli et al 2008c; Cohen's $d: -0.61$; Vrieze et al 2013a). In contrast, euthymic individuals with bipolar disorder had significantly higher reward learning relative to controls (Cohen's $d: 0.72$) (Pizzagalli et al 2008b). For the reinforcement learning task proposed for our fMRI study (Pessiglione et al 2006), we found that, relative to healthy controls, MDD subjects had significantly lower accuracy during reward learning (Cohen's $d: -1.54$). These effect sizes translate to power >0.98 for detecting group differences with the proposed sample size. For dimensional approaches, past studies have shown a strong large effect for the relationship between reward learning and anhedonic symptoms in BPD patients ($r = -0.59$). Moreover, among healthy subjects, reward learning predicted anhedonic symptoms 30-40 days later ($r = -0.41$, $p < 0.05$). In light of these effect sizes, a total of 80 individuals with mood disorders leads to a power of >0.97 of (1) detecting relationships between units of analysis and reward-related symptoms (e.g., anhedonia, mania), and (2) predicting clinical outcome in the naturalistic follow-

up study. Finally, in an fMRI study probing reward processing, unmedicated MDD subjects showed weaker activation than controls to gains in the caudate ($d = -0.98$) and left Nac ($d = -0.73$) and left putamen ($d = -0.78$) during reward anticipation (Pizzagalli et al 2009), yielding a mean effect size of -0.87. In light of an average ES of 0.83 in the fMRI study, a total of 80 individuals with mood disorders and 32 healthy controls leads to a power >0.97 of detecting group differences.

VII. RISKS AND DISCOMFORTS

The risks associated with participation in this study are minimal, and every possible precaution is being taken to further reduce potential risks, as described below:

Behavioral component. We foresee no risks from the behavioral tasks required for the proposed research.

Genetic component.

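### The group-difference power in VI.d applies effects from a single diagnosis to all 80 patients, who are an unspecified mix of unipolar and bipolar; the fMRI and PRT figures should be restated

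*Combined protocol and SAP*

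**What the plan says.** Section VI.d sets alpha at 0.05 two-sided, allows 15% patient attrition or data loss, and arrives at 80 patients and 32 controls. For group comparisons it cites these effects:

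- **PRT, MDD v control:** d = -0.70 and -0.61.
- **PRT, bipolar v control:** d = +0.72, introduced with "In contrast, euthymic individuals with bipolar disorder had significantly higher reward learning relative to controls".
- **Reinforcement-task accuracy, MDD v control:** d = -1.54.
- **fMRI, MDD v control:** the source is a study in which "unmedicated MDD subjects showed weaker activation than controls to gains in the caudate" (d = -0.98), with -0.73 in the left accumbens and -0.78 in the left putamen.

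After the behavioural effects it states: "These effect sizes translate to power >0.98 for detecting group differences with the proposed sample size". After the fMRI effects it states that "a total of 80 individuals with mood disorders and 32 healthy controls leads to a power >0.97 of detecting group differences".

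The 80 are not of one diagnosis. The inclusion criteria in III.a name a depression program together with the "MGH Bipolar Clinical and Research Program (BCRP), and McLean Hospital Bipolar Disorder Program". Section VIII describes the patients as having unipolar or bipolar depression. No expected number of each is given. Section I (Previous research) adds that, at group level, "patients with unipolar and bipolar diagnoses show attenuated and potentiated reward learning during this task, respectively".

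**The concern.** A power figure for 80 v 32 at an MDD effect size is the power of a comparison in which all 80 patients have MDD. This sample allows two other comparisons. One takes patients of a single diagnosis against the 32 controls, with fewer than 80 in the patient arm. The other pools all patients, and its effect is a weighted mean of the unipolar and bipolar effects. VI.d gives power for neither.

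The figures are part of the stated support for the sample size, and section V describes the controls as recruited for comparison with the patients. A reader who takes >0.97 at face value would treat a null pooled patient-control result as a well-powered negative, when dilution by a smaller bipolar effect could produce it.

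**Working it through.** **Inputs.** Two-sided alpha 0.05; 80 patients and 32 controls; 68 patients after 15% loss (80 x 0.85); the effect sizes listed above (all VI.d). The proposed sample size behind >0.98 is read as 80 v 32. The fMRI mean is (0.98 + 0.73 + 0.78)/3 = 0.83. VI.d prints both -0.87 and 0.83; 0.83 is the arithmetic mean and is the value used for its power.

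**Method for two arms.** Two-sample t test, noncentrality = d x sqrt(n1 n2/(n1 + n2)), with n1 + n2 - 2 degrees of freedom.

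**Step 1: the plan's own figures.** For fMRI, 0.83 x sqrt(80 x 32/112) = 3.97, power 0.976. At 68 v 32 the noncentrality is 3.87 and power 0.970. So >0.97 reproduces when every patient carries the MDD effect. For >0.98 at 80 v 32:

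| Effect | Power |
|---|---|
| PRT, d = 0.61 | 0.82 |
| PRT, d = 0.70 | 0.91 |
| PRT, d = 0.72 | 0.93 |
| Task accuracy, d = 1.54 | >0.99 |

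None of the three PRT effects reaches 0.98, even with all 80 patients. A d of about 0.85 would be needed.

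**Step 2: one diagnosis v 32 controls.** The split is not given, so these counts are assumptions.

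| Patients of that diagnosis | fMRI 0.83 (MDD) | PRT 0.61 (MDD) | PRT 0.70 (MDD) | PRT 0.72 (bipolar) |
|---|---|---|---|---|
| 27 | 0.88 | 0.63 | 0.75 | 0.77 |
| 40 | 0.93 | 0.72 | 0.83 | 0.85 |
| 53 | 0.96 | 0.77 | 0.87 | 0.89 |

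At 64 unipolar patients (80% of the 80) the fMRI figure is 0.967. Task accuracy at d = 1.54 stays above 0.99 at 27, 40 and 53.

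**Step 3: all patients pooled, 80 v 32.** For unipolar share w, net d = w x d_uni + (1 - w) x d_bip. The patient variance is 1 + w(1 - w)(d_uni - d_bip)^2. Power is from a normal-approximation Welch test.

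Worked example, fMRI with w = 0.5 and a bipolar effect of zero: net d = -0.415; variance = 1 + 0.25 x 0.83^2 = 1.172; standard error = sqrt(1.172/80 + 1/32) = 0.214; z = 1.94; power 0.49.

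For the PRT, d_uni = -0.655 (the mean of -0.70 and -0.61) and d_bip = +0.72.

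| Unipolar share | fMRI, bipolar effect half of MDD | fMRI, bipolar effect zero | PRT, signs as in VI.d (net d) |
|---|---|---|---|
| 1/3 | 0.75 | 0.25 | 0.22 (+0.26) |
| 1/2 | 0.84 | 0.49 | 0.05 (+0.03) |
| 2/3 | 0.91 | 0.74 | 0.15 (-0.20) |
| 0.8 | 0.94 | 0.88 | 0.41 (-0.38) |

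The bipolar fMRI effects are assumptions, because the documents give none.

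**Step 4: the sign of the bipolar PRT effect.** Section I and VI.d say bipolar patients are higher than controls. The title of the cited study in the reference list (section X) says reward learning was decreased. If both diagnoses are reduced (-0.655 and -0.72), pooled PRT power is about 0.9 and the cancellation disappears, but 0.98 is still not reached.

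**The case against.** The strongest reply is that no patient-control test is planned. VI.c specifies regression, canonical correlation and mixed models; the hypotheses are dimensional or predictive; Aim 1 calls the controls a reference point. VI.d also lists unit-symptom relationships and follow-up prediction as the purposes of the sizing, with a separate power claim that this point does not touch. This stands. It limits the consequence, and it is a reason not to impose a three-level diagnostic factor on a study that sets out to avoid reliance on DSM categories. It does not make the printed group-difference figures right.

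The fMRI shortfall can also be modest. Recruitment extends to the community and to McLean depression clinics (III.b, IV.a), and the one-third quota in Aim 1 can be met by severe depression, so no bipolar minimum is set. With 64 unipolar patients the MDD-only figure is 0.967, close to what is printed. This stands too, and is why the assumed share runs up to 0.8. Since 0.976 reproduces, the fMRI fault is in the assumption and not in the arithmetic.

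A reader might infer that unipolar and bipolar effects cancel throughout, so that pooled power is negligible for fMRI as well. The documents do not support that. Opposite signs are stated for the PRT only, and no bipolar fMRI effect appears anywhere. Even for the PRT, the +0.72 comes from euthymic patients, whereas IV.a enrols patients with current symptoms, and it conflicts with the cited title.

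**Conclusion.** The point holds as a fault in the stated power, not in the design. The fMRI figure of >0.97 requires bipolar patients to share essentially the whole MDD deficit. Otherwise it is 0.88 to 0.967 for MDD alone (27 to 64 patients). Pooled, for unipolar shares of 1/3 to 0.8, it is about 0.75 to 0.94 if the bipolar effect is half the MDD effect and 0.25 to 0.88 if it is zero. The >0.98 is wrong for all three PRT effects at 80 v 32, and they give 0.63 to 0.89 at 27 to 53 patients of one diagnosis. Pooled PRT power of about 0.05 to 0.4 follows only if the +0.72 stands with its sign. The >0.98 is supported for MDD task accuracy alone.

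These ranges rest on assumed splits and assumed bipolar fMRI effects. The PRT figures also take the published d at face value, although the 80 are selected as 16 per normative PRT quintile, which pulls the screening PRT mean towards that of controls whatever the diagnosis.

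**What to change.** In VI.d:

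1. State that each group effect is a single-diagnosis contrast with controls.
2. Replace the 80 v 32 figures for fMRI and the PRT with power at the expected number of patients of that diagnosis, or a range if the split is unknown (for example, fMRI 0.88 to 0.967 at 27 to 64 unipolar patients).
3. Keep >0.98 only for task accuracy in MDD v control.
4. Note that the PRT figures do not allow for the 16-per-quintile selection.
5. Reconcile the direction of the bipolar PRT effect between section I, VI.d and the cited title.
6. State that a null pooled patient-control difference is not a well-powered negative.

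A comparison by SCID diagnosis can be offered as a secondary description, since the diagnosis is already collected; it need not be mandatory.

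The cost is a few sentences in VI.d and a less favourable printed power. No extra patients or procedures are needed, and the dimensional power claim stays as it is.
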